9.1 Subject Confidentiality

All participants are concerned for the individual subject's privacy and, therefore, all subject data will be identified only by a subject identification number and subject initials. However, in compliance with federal guidelines regarding the monitoring of clinical studies and in fulfillment of his/her obligations to Perrigo, it is required that the investigator permit the study monitor, any Perrigo authorized representative, and/or FDA representative to review that portion of the subject's medical record that is directly related to the study. This shall include all study relevant documentation including subject medical histories to verify eligibility, laboratory test result reports to verify transcription accuracy, admission/discharge summaries for hospital stays occurring while the subject is enrolled in the study and autopsy reports for deaths occurring during the study.

As part of the required content of informed consent, the subject must be informed that his/her medical chart may be reviewed by Perrigo or their authorized representative, or a representative of the FDA. Should access to the medical record require a separate waiver or authorization, it is the investigator's responsibility to obtain such permission from the subject in writing before the subject is entered into the study.

To preserve the subject's confidentiality, the data collected will be available only to the investigators of the study, their support staff, Perrigo or their authorized representative and possibly the FDA.

All reports and communications relating to the subject in the study will identify each subject only by the subject's initials and by the subject number. The investigator agrees to furnish Perrigo with complete subject identification, if necessary on a confidential follow-up form, which will be used for the purpose of a long-term follow-up, if needed. This will be treated with strict adherence to professional standards of confidentiality and will be filed at Perrigo under adequate security and restricted accessibility.

9. CONDUCT OF STUDY

The investigational site is to maintain complete documentation of all events and the times at which they occur.

10.1 Completion of Study

The investigational site will complete the study and complete all documentation required, in satisfactory compliance with the protocol, within 3.5 months of enrollment of the last subject and extending beyond as needed to complete necessary data queries.

It is agreed that, for reasonable cause, either the investigator or Perrigo may terminate this study before completion provided written notice is submitted at a reasonable time in advance of intended termination. Any extension of this study must be mutually agreed upon in writing by both the investigator and Perrigo.

10.2 Protocol Amendments

The Investigator will not make any changes to this protocol without prior written consent from Perrigo and subsequent approval by the IRB. Any permanent change to the protocol, whether it is an overall change or a change for specific study center(s), must be handled as a protocol amendment. Any amendment to the protocol that appears indicated as the study progresses will be fully discussed between [REDACTED] and Perrigo. If agreement is reached regarding the need for an amendment, the amendment will be written by Perrigo. The written amendment must be submitted to the chairman of the IRB identified with this responsibility. Except for 'administrative amendments,' investigators must await IRB approval of protocol amendments before implementing the change(s). Administrative amendments are defined to have no effect on the safety of the research subjects, scope of the investigation, or quality of the trial. However, a protocol change intended to eliminate an apparent immediate hazard to subjects should be implemented immediately, and the IRB notified within five days. Perrigo will submit protocol amendments to the FDA or other regulatory agencies.

When, in the judgment of the reviewing IRB, the investigators and/or Perrigo, the amendment to the protocol substantially alters the study design and/or increases the potential risk to the subject, the currently approved written informed consent form will require similar modification. In such cases, repeat informed consent will be obtained from subjects enrolled in the study before expecting continued participation.

11. RECORDS MANAGEMENT

11.1 Data Collection

CRFs for individual subjects will be provided [REDACTED]. CRFs must be legible and complete. CRFs for this study will be maintained in a study binder and data recorded on 2-part NCR paper. One copy will be kept by the investigator and the other copy will be submitted to the CRO data management group. All forms should be completed using a black ballpoint pen. Errors should be lined out, but not obliterated, and the correction inserted, initialed, and dated by designated study personnel. Further

Protocol No: PRG-NY-16-009

data corrections will be performed on data correction forms (DCFs) that will be provided by the CRO to the investigator in case of erroneous or unclear data. The investigator will make the correction on the DCF and sign the DCF. The signed DCF will be submitted to the CRO data management group for processing and a copy retained with the CRFs.

A CRF must be completed and signed by the investigator for each subject enrolled, including those discontinued from the study for any reason. The reason for discontinuation must be noted on a subject's study termination form.

CRFs must be kept current to reflect the subject's status at each phase during the course of the study. Subjects are not to be identified on CRFs by name; appropriately coded identification and the subject's initials must be used. The investigator must keep a separate log of the subject's names and addresses.

During each subject's visit to the clinic, a designee participating in the study will record progress notes to document all significant observations. At a minimum, these notes will contain:

- a) Documentation of the informed consent process;
- b) The date of the visit and the corresponding Visit or Week in the study schedule;
- c) General subject status remarks, including any significant medical findings. The severity, frequency, and duration of any adverse events and the investigator's assessment of relationship to study medication must also be recorded.
- d) Any changes in concomitant medications or dosages;
- e) A general reference to the procedures completed; and
- f) The signature (or initials) and date of all clinicians who made an entry in the progress notes.

In addition, any contact with the subject via telephone or other means that provides significant clinical information will also be documented in the progress notes as described above.

Any changes to information in the study progress notes and other source documents, will be entered in **black ink**, **initialled** and **dated** by the authorized person making the correction/addition. Changes will be made by striking a single line through erroneous data, and clearly entering the correct data. (e.g., ~~wrong data~~ right data). Entries may not be erased or masked with white-out fluid. If the reason for the change is not apparent, a brief explanation for the change will be written adjacent to the change by the clinician.

For transmission to Perrigo, information from the study progress notes and other source documents will be promptly entered into the database. The database also contains a complete audit trail to capture all regulatory components of data correction (e.g., initial entry, new value, initials and date of the change).

11.2 Source Documents

Source documents are defined as the results of original observations and activities of a clinical investigation. Source documents will include, but are not limited to, progress notes and screening logs. All source documents pertaining to this study will be maintained by the investigators and made available for inspection by authorized persons. The original signed informed consent form for each

Protocol No: PRG-NY-16-009

participating subject shall be filed with records kept by the investigators and a copy given to the subject.

11.3 File Management at the Study Site

It is the responsibility of the investigator to ensure that the study center file is maintained in accordance with Section 8 of the International Conference on Harmonization (ICH) Guideline for Good Clinical Practices (GCP).

11.4 Records Retention at the Study Site

FDA regulations 21 CFR §312.57 require all investigators participating in clinical drug studies to maintain detailed clinical data for one of the following periods:

- a) A period of at least two years following the date on which a New Drug Application is approved by the FDA;
- b) A period of two years after Perrigo notifies the investigator that no further application is to be filed with the FDA.

The investigator must not dispose of any records relevant to this study without either (1) written permission from Perrigo or (2) providing an opportunity for Perrigo to collect such records. The investigator shall take responsibility for maintaining adequate and accurate electronic or hard copy source documents of all observations and data generated during this study. Such documentation is subject to inspection by Perrigo and the FDA.

12. QUALITY CONTROL AND QUALITY ASSURANCE**12.1 Monitoring**

Perrigo has ethical, legal and scientific obligations to carefully follow this study in a detailed and orderly manner in accordance with established research principles and FDA regulations. All medical records (source documents) of the subjects participating in this study must be presented for review and verification of CRFs.

12.2 Auditing

Perrigo (or representative) may conduct audits at the study center(s). Audits will include, but are not be limited to, drug supply, presence of required documents, the informed consent process, and comparison of CRFs with source documents. The investigator agrees to participate with audits conducted at a reasonable time in a reasonable manner.

Regulatory authorities worldwide may also audit the investigator during or after the study. The investigator should contact Perrigo immediately if notified of such an audit, and must fully cooperate with the audits conducted at a reasonable time in a reasonable manner.

13. ETHICS AND RESPONSIBILITY

This study must be conducted in compliance with the protocol, the United States Food and Drug Administration (FDA) regulations, any other countries regulations, and ICH GCP Guidelines.

The purpose of the statistical analysis plan is to describe in detail all the data, statistical methods, and summary tables required to implement the statistical analysis of Clinical Study Protocol PRG-NY-16-009 ([REDACTED]).

2 Study Objectives

To compare the safety and efficacy profiles of Perrigo UK FINCO's Azelaic Acid Foam, 15%, to Bayer HealthCare Pharmaceuticals Inc., Finacea® (Azelaic Acid) Foam, 15%, in order to prove bioequivalence between them and to demonstrate the superior efficacy of the two active formulations over that of the vehicle in the treatment of Inflammatory Lesions of Rosacea.

3 Study Design and Sample Size

3.1 Study Design

For the purpose of exploring the above objectives, the study will be conducted as a double-blind, randomized, parallel-group, vehicle-controlled, multicenter trial.

Each subject will be randomly assigned to one of the following treatment groups in a [REDACTED]

- (1) Test: Azelaic Acid Foam, 15%, [REDACTED]
- (2) Reference: Finacea® (Azelaic Acid Foam, 15%) manufactured by Bayer HealthCare Pharmaceuticals Inc.
- (3) Vehicle of test product, [REDACTED].

Subjects will be admitted into the study only after written informed consent has been obtained and all of the inclusion and none of the exclusion criteria have been met. Randomization will be performed according to a computer generated randomization scheme where the treatment group designation has been assigned to the subject number. The treatment designation will remain blinded until after the final database is locked. An independent third party will generate and hold the randomization code throughout the study. Randomized subjects will apply the smallest amount of the assigned study medication necessary as a thin layer to adequately cover each area of the face (chin, left cheek, right cheek, nose, and forehead), avoiding contact with the eyes (upper and lower eyelids), lips, broken skin, inside the nose/nostrials and mucous membranes, twice daily morning and evening ([REDACTED]) approximately the same time for 12 weeks..

Subjects will come to the study site for clinical evaluations at Visit 1/Day 1 (Baseline), Visit 2/Interim/Week 4 (Day 28 ±4 days), Visit 3/Interim/Week 8 (Day 56 ±4 days), and Visit 4/End of Treatment/ Week 12 Study (Day 84 ±4 days) or at early discontinuation. Safety will be assessed by monitoring adverse events at each visit and at the Week 2/Day 14 (±4 days) Telephone Contact.

3.2 Sample Size

Approximately [REDACTED] subjects will be randomized in ratio [REDACTED] (Test:Reference:Vehicle) to obtain [REDACTED] mITT subjects and [REDACTED] PP subjects. This sample size

[REDACTED]

[REDACTED]

The actual number of subjects enrolled in the study will be based on blinded review of subject status (related to the per-protocol definition, section 4) to determine that the number of subjects expected to meet the PP criteria is sufficient ([REDACTED]). If this number is expected to be met prior to enrolling [REDACTED] subjects, the enrollment will be closed.

4 Populations To Be Analyzed

The analysis populations are defined as follows:

- (1) Intent-to-treat (ITT) population: any subject that was randomized, received and used study medication;
- (2) Modified Intent-to-treat (mITT) population: any subject, who met the inclusion/exclusion criteria, was randomized, received and used the study medication, and returned for at least one post-baseline efficacy assessment;
- (3) Per Protocol (PP) population: any subject who (a) met all inclusion/exclusion criteria; (b) was randomized and received and used study medication; (c) met the protocol criteria for compliance [REDACTED]; (d) completed Visit 4/Week 12/Day 84 (End of Treatment/Early Termination Visit) within window OR was discontinued from the study due to treatment failure and; (e) Without significant protocol violations that could have interfered with the administration of the treatment or the precise evaluation of treatment efficacy.

[REDACTED]

[REDACTED]

[REDACTED]

[REDACTED]

[REDACTED]

[REDACTED]

5 Planned Analyses

5.1 Methodological Considerations

The study will be conducted under the same protocol across all the sites. No formal statistical analyses are planned to evaluate the consistency of efficacy results across the multiple clinical sites. These results, however, will be tabulated and if a site's efficacy data are obviously inconsistent with the results across all sites, this will be explored and addressed in the final study report.

All randomized subjects who received study medication will be evaluated for safety using ITT population. The efficacy analysis will be conducted on both the PP and the mITT populations.

Two-sided hypothesis testing will be conducted for all the tests. Resulting p-values less than 0.05 will be considered statistically significant unless noted otherwise. No adjustments of p-values for multiple comparisons will be made. No interim analyses are planned.

SAS software will be used for all data analyses and tabulations.

5.2 [REDACTED]

[REDACTED]

[REDACTED]

5.3 Demographics and Baseline Characteristics

Baseline variables (e.g., sex, age, ethnic origin) will be analyzed by adjusting for site, to identify differences between treatment groups. Any significant baseline differences will be reviewed for their potential impact on the efficacy findings.

Continuous variables at baseline will be examined by two-way analysis of variance (ANOVA) with treatment and site as fixed effects when ANOVA assumptions (normally distributed error, homogeneous variance) are satisfied, or by the nonparametric rank test when ANOVA assumptions are not met.

Categorical variables such as gender, race, etc., will be examined by Cochran-Mantel-Haenszel test, stratified by site. Summary tables by treatment group will be presented. For each continuous

variable, the summary will include the mean, standard deviation, minimum and maximum. For each categorical variable, the summary will include frequencies and percentages.

5.4 Subject Accountability

A summary of subject disposition will be provided for all subjects. Descriptive summaries of subject disposition, reason for discontinuation, and analyses population will be provided by treatment group. The data will also be presented in subject data listings.

5.5 Efficacy Variables and Analyses

5.5.1 Primary Endpoint

The primary efficacy endpoint of the study is the mean percent change from baseline to Visit 4/Week 12 in the inflammatory (papules and pustules) lesion counts.

Equivalent Efficacy

For the mean percent change from baseline in the inflammatory lesion counts, the Test treatment will be considered to be therapeutically equivalent to the Reference treatment if the 90% confidence interval on the Test-to-Reference ratio of means, calculated by Fieller's Method, falls within the interval 0.80 to 1.25. The compound hypothesis to be tested for therapeutic equivalence between test and reference is:

$$H_0: \mu_T/\mu_R \leq 0.80 \text{ or } \mu_T/\mu_R \geq 1.25 \text{ versus}$$

$$H_A: 0.80 < \mu_T/\mu_R < 1.25.$$

Where μ_T and μ_R are the mean percent change from baseline to Visit 4/Week 12 (Day 84) in inflammatory lesions counts for the test treatment and the reference treatments, respectively. The null hypothesis is rejected when the two-sided 90% confidence interval (CI) for the ratio of means between test and reference products is between 0.80 and 1.25. Rejection of the null hypothesis supports the conclusion of therapeutic equivalence between test and reference products for the primary efficacy variable.

The two-sided 90% confidence interval will be constructed using an ANOVA model with treatment and site as factors.

The therapeutic equivalence evaluation in the per-protocol (PP) population will be considered definitive and that in the mITT will be considered supportive.

Analysis for therapeutic equivalence will be performed based on the following SAS code (SAS Institute v.9.1.3):

The key procedure used to determine CIs for ratio of treatment means:

```

PROC GLM DATA=inf_pp;
  CLASS trt site;
  MODEL pchg_inf = trt site;
  ESTIMATE 'ratio=c' intercept (1-c) trt 1 -c;
RUN;

```

Where the ESTIMATE statement is run targeting at two-sided $p=0.10$ to locate the c value (our Test/RLD) for the 90% CI.

Superiority

For the percent change from baseline in the inflammatory lesion counts, each active treatment will be evaluated to determine if it has superior efficacy to that of the Vehicle at Visit 4/Week 12 (Day 84) via an ANOVA model containing terms for treatment and site. The compound hypothesis to be tested for superiority of test and reference over Vehicle is:

$H_0 : \mu_T \leq \mu_V \text{ or } \mu_R \leq \mu_V$ versus

$H_A : \mu_T > \mu_V \text{ and } \mu_R > \mu_V$

Where μ_T , μ_R and μ_V are the mean percent change from baseline to Visit 4/Week 12 (Day 84) in inflammatory lesions counts for the test, the reference and the vehicle treatments, respectively. The null hypothesis is rejected when both p -values from the ANOVA are less than 0.05 (two-sided test). Rejection of the null hypothesis supports the conclusion of superiority of test and reference products over the vehicle product for the primary efficacy variable.

A skewness test (SAS® PROC UNIVARIATE) will be performed using the residuals from the ANOVA of the primary efficacy variable. If the skewness statistic is greater than 2 or less than -2, the analysis will be performed on the ranked mean percent change from baseline to Visit 4/Week 12 (Day 84) in inflammatory lesion counts.

Superiority analyses in the mITT population will be considered definitive and those in the PP will be considered supportive.

Analysis for superiority will be performed based on the following SAS code (SAS Institute v.9.1.3):

The key procedure used to compare mean values of an active treatment arm to vehicle:

```

PROC GLM DATA=inf_pp;
  CLASS trt site;
  MODEL pchg_inf = trt site /ss3;
RUN;

```

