8.1.3 Sample Size Considerations

8.1.4 Efficacy Measures and Analysis

Clinical endpoints

The primary efficacy measure will be the mean percent change from baseline to Visit 4/Week 12 (Day 84) in the inflammatory (papules and pustules) lesion counts. The secondary efficacy measure will be the proportion of subjects with clinical success defined as a score of clear or almost clear (score of 0 or 1) on the Investigator Global Assessment (IGA) at Visit 4/Week 12 (Day 84).

Equivalent efficacy

For the mean percent change from baseline in the inflammatory lesion count, the Test treatment will be considered to be therapeutically equivalent to the Reference treatment if the 90% confidence interval on the Test-to-Reference ratio of means, calculated by Fieller's Method, falls within the interval 0.80 to 1.25. The treatment means and estimate of residual variance for the confidence interval calculation will come from an Analysis of Variance of the Test and Reference results using a statistical model containing terms for Treatment and Site.

For the proportion of subjects with clinical success, the Test treatment will be considered to be therapeutically equivalent to the Reference treatment if the 90% confidence interval on the difference between Test and the Reference proportions is contained within the interval -20% to +20%. The confidence interval will be constructed using Wald's method with Yates' continuity correction.

Therapeutic equivalence evaluations in the per-protocol (PP) population will be considered definitive and those in the mITT will be considered supportive.

Superiority

For the mean percent change from baseline in the inflammatory lesion count, each active treatment will be evaluated to determine if it has superior efficacy to that of the Vehicle at Visit 4/Week 12 (Day 84) via an Analysis of Variance using Proc Mixed of SAS with Treatment and Site as factors.

The proportion of subjects with clinical success for each active treatment will be compared to that of the Vehicle using Z-test with Yate's continuity correction.

Superiority tests will be two-sided at a significance level of $\alpha = 0.05$. Superiority analyses in the mITT population will be considered definitive and those in the PP will be considered supportive

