Where p_T , p_R and p_V are the proportions of subjects with clinical success at Visit 4/Week 12 (Day 84) for the test, reference and Vehicle products, respectively. The tests will be conducted independently for the test product vs. vehicle and the reference product vs. vehicle using two-sided, $\alpha = 0.05$, continuity-corrected Z-tests. Superiority will be established if the

proportion of subjects with clinical success in the active treatment group is greater than and statistically different ($p < 0.05$) from that in the Vehicle. Rejection of the null hypothesis supports the conclusion of superiority of the test and reference products over the Vehicle product for the secondary efficacy variable.

The analyses in the mITT population will be considered primary and those in the PP population as supportive.

Analysis for superiority will be performed based on the following SAS code (SAS Institute v.9.1.3):

The SAS code for p-value (trt=2 for Reference vs. trt=3 for Vehicle):

```
proc freq data=XX ;  
  where trt in (2,3);  
  table trt * success /chisq ;  
run;
```

5.5.3

[REDACTED]

[REDACTED]

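### Does the primary superiority rule in SAP 5.5.1 need an explicit direction condition and a stated sign for percent change?

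*SAP*

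**What the plan says.** SAP 5.5.1 (Superiority) says each active is assessed for better efficacy than Vehicle by an ANOVA with treatment and site. It continues: "The compound hypothesis to be tested for superiority of test and reference over Vehicle is" H0: μT ≤ μV or μR ≤ μV, against HA: μT > μV and μR > μV. The symbols "are the mean percent change from baseline to Visit 4/Week 12 (Day 84) in inflammatory lesions counts for the test, the reference" and vehicle arms. H0 is rejected when both p-"values from the ANOVA are less than 0.05 (two-sided test"), and the next sentence reads: "Rejection of the null hypothesis supports the conclusion of superiority of test and reference products over the vehicle product for the primary efficacy variable".

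The printed model line is "MODEL pchg_inf = trt site /ss3", with no statement asking for a signed active-minus-vehicle difference.

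Protocol 8.1.4 adds only this on sidedness: "Superiority tests will be two-sided at a significance level of" 0.05.

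For the secondary endpoint, SAP 5.5.2 declares superiority if the "proportion of subjects with clinical success in the active treatment group is greater than and statistically different" from that in Vehicle at p < 0.05.

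On the variable itself, SAP 5.5.1 says: "The primary efficacy endpoint of the study is the mean percent change from baseline to Visit 4/Week 12" in inflammatory lesion counts. No visible formula follows. SAP 5.2 and 5.5.3 are blacked out.

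**The concern.** A two-sided p-value is the same whether the active arm is better or worse than Vehicle. The secondary rule deals with this by naming the direction; the primary rule does not. Taken word for word, two actives significantly worse than Vehicle would satisfy the condition for a superiority claim on the primary endpoint.

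A reader who turns to HA for the missing direction meets a second difficulty. If percent change is (Week 12 − baseline)/baseline, benefit is negative and the inequality in HA points the wrong way. It points the right way only if the variable is coded as a percent reduction, which no visible text states. The printed code does not settle the matter, because its F test for treatment has no sign.

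At stake would be the validity of one of the two primary claims. A rule that can be met from the wrong side does not control error over its own null.

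**Working it through.** The plan gives no visible figure to reproduce: sample size, allocation, SD and power are blacked out. The documents supply α = 0.05 two-sided (critical value 1.960, so 0.025 in each tail) and the requirement that both comparisons succeed. Allocation ratios, arm sizes, effect and SD below are assumptions.

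**1. Does the sign convention change any result?** Take a baseline of 20 lesions, with active falling to 5 and vehicle to 12.

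- As (post − baseline)/baseline: active −75%, vehicle −40%, so the better arm has the smaller value.
- As (baseline − post)/baseline: active +75%, vehicle +40%, so the better arm has the larger value, as HA requires.

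Switching conventions multiplies every value by −1. The t statistic becomes −t, and |t| and the two-sided p-value stay the same. The Test-to-Reference ratio is unchanged, since (−a)/(−b) = a/b, and so is its Fieller interval. The residual skewness changes sign, but the trigger for ranking (above 2 or below −2) is symmetric, so the same branch is taken. Ranks reverse, and the two-sided p-value on ranks is unchanged.

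**2. How often would the literal rule be met wrongly?** The two active-versus-Vehicle statistics share the Vehicle arm, with correlation

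ρ = (1/nV) / √[(1/nT + 1/nV)(1/nR + 1/nV)],

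which is k/(k+1) for allocation k:k:1. The bivariate normal probabilities of rejection are:

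| Allocation | ρ | All arms equal: literal rule | All arms equal: with direction | One active equal to Vehicle, other far better: literal / with direction |
|---|---|---|---|---|
| 1:1:1 | 0.50 | 0.0093 | 0.0046 | 0.050 / 0.025 |
| 2:2:1 | 0.667 | 0.0151 | 0.0075 | 0.050 / 0.025 |
| 3:3:1 | 0.75 | 0.0190 | 0.0095 | 0.050 / 0.025 |

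With all arms equal, half of the literal total has both actives significantly worse: 0.5% to 1.0% of trials. In the last column, the extra 0.025 comes from trials in which one active is significantly worse than Vehicle. If both actives were truly worse by 2.8 standard errors, the literal rule would be met in 69% to 72% of trials. That is the mirror image of the result the trial hopes for.

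**3. Does a direction clause cost or gain power?** Assume 200:200:100, SD 40 and both actives 15 points better. Then SE = 40 × √(1/200 + 1/100) = 4.90 and 15/4.90 = 3.06. Both comparisons succeed in 79% of trials, with or without the clause.

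**4. Reading the sentence in place.** The rejection sentence is the decision step for the hypotheses printed just before it. With > read as benefit, two actives worse than Vehicle belong to H0, so announcing superiority would contradict the SAP's own null. The sentence after the rule equates rejection with superiority, which makes sense only if > means benefit. The rule also speaks of two p-values, one per active arm. A single overall treatment F test cannot supply these, so the analyst must make pairwise comparisons in any case, and the direction is visible in the means compared.

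**The case for a change.** The best case for a change is that a decision rule should be complete in itself. SAP 5.5.2 shows that its authors knew how to write the direction clause, and 5.5.1 lacks it. HA cannot fully stand in for the clause while the coding of percent change is unseen. Even if the blacked-out sections define the variable, the rejection sentence is visible in full and still has no direction. The repair would cost one clause and no power.

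All of that stands as a description of the text. What does not follow is a consequence. For the gap to matter, an analyst would have to see both actives significantly worse than Vehicle, ignore the stated aim of showing superior efficacy (Protocol 2, SAP 2), ignore the summaries of response by treatment group promised in Protocol 8.1.2, and report superiority. One of the two actives is a product already indicated for this condition (Protocol 1), and nothing in the documents suggests that either is worse than Vehicle. The 69% to 72% figure needs that premise. The missing formula cannot be held against the plan, because it may lie in the blacked-out SAP 5.2 or 5.5.3.

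**Conclusion.** The concern does not call for a change. SAP 5.5.1 omits a clause that SAP 5.5.2 contains, and the visible text leaves the sign of percent change unstated. Direction is nonetheless fixed by the alternative hypothesis, by the study objective and by the conclusion attached to rejection, and every analyst would apply it. The p-values, the equivalence ratio and its interval, and the choice between raw and ranked analysis are the same under either coding. Power is the same with or without the clause (79% under the assumed inputs). The literal excess with all arms equal is 0.5% to 1.0% over the assumed allocations; in the boundary case with one active equal to Vehicle it is 0.025. Neither would survive a look at the group means. Matching the wording to 5.5.2 would be harmless tidying that alters no realistic result or conclusion. This rests on reading the rejection sentence together with the hypotheses it serves, and on not treating blacked-out definitions as absent.
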